5.5 Patient Discontinuation

All study participants have the right to withdraw from the study at any time.

The investigator has the right to discontinue a patient from the study for any medical condition that the investigator determines may jeopardize the patient's safety if he or she continues in the study and for reasons of non-compliance (eg, missed doses, visits) or pregnancy or if the investigator determines it is in the best interest of the patient.

Any patient who discontinues treatment but does not withdraw informed consent should be encouraged to return to the study site for a treatment completion visit. See [Appendix 1](#) for the assessments that are to be performed for patients who prematurely withdraw from the study during the treatment period. The primary reason for discontinuation must be recorded on the appropriate CRF. Patients discontinuing surufatinib for reasons other than progression of the underlying malignancy are to continue tumor assessments per [Appendix 1](#), until documentation of disease progression, start of new anti-tumor therapy, or withdrawal of informed consent.

5.6 Overall Survival Follow Up

Overall survival is defined as the time from the date of the first dose of study drug until the date of patient death (any cause). Investigators and/or delegated site staff should follow patients enrolled to the BTC and STS expansion cohorts, who have signed informed consent under sponsor Amendment 8 (or later), until death or until the patient is lost to follow up. Follow up for OS will begin after the end of treatment (EOT) visit has been completed. Patients should be followed every 8 weeks (\pm 2 weeks) via telephone or in a manner that follows local site SOPs. Site staff should attempt to contact a patient 3 times and consult with authorized family members for the status of the patient (when applicable) before considering a patient lost to follow up. Data to be collected should include the date the patient was last known to be alive, the date of death, and the cause of death.

Treatment completion of patients will occur if any of the following 3 criteria is met:

1. Disease progression (according to RECIST Version 1.1), unless there is reasonable evidence of clinical benefit to justify continuation on the study drug. The continuation decision should be made by the investigators in consultation with the sponsor. The disease progression date is the date when radiological disease progression is first reported according to RECIST Version 1.1 criteria;
2. Death;
3. End of this study.

Early discontinuation of study drug will occur if any of the following criteria is met:

1. Patient withdrawal of informed consent;
2. Intolerable toxicity;
3. Poor patient compliance;
4. Use of other antitumor treatment during the study;
5. Pregnancy occurred during the study treatment period;
6. Patient is lost to follow-up;
7. Treatment discontinuation is in the best interest of the patient based on the assessment of the investigator and sponsor.

5.7 Study Discontinuation

Hutchison MediPharma has the right to stop the study at any time. The reasons for stopping the study may include, but are not limited to, the following:

- The incidence or severity of adverse events in this or other studies indicates a potential health hazard to patients.
- Patient enrollment is unsatisfactory.

5.8 End of Treatment (Individual Patient)

5.8.1 End of Study

A subject is considered to have completed the study once he or she has completed the last visit or the last scheduled procedure as outlined in the Schedule of Events ([Table 12](#)).

5.8.2 Study Completion Date

The study will be considered completed once the following has occurred:

- The last subject has completed the last visit or last scheduled procedure.

6 PATIENT SELECTION

Patients with locally advanced or metastatic solid tumors for whom approved therapy either does not exist or has proven to be ineffective or intolerable are eligible to participate in the dose escalation phase of this study. Patients will undergo a screening period of up to 4-weeks, during which they will be assessed for compliance with the inclusion and exclusion criteria as outlined below.

6.1 Inclusion Criteria

To be eligible to participate in the study, patients must meet all of the following criteria:

1. Fully understand the study and voluntarily sign the ICF;
2. At least 18 years old;
3. Dose escalation phase: Histologically or cytologically documented, locally advanced or metastatic solid malignancy of any type, that has progressed on available standard systemic therapy, and for which no effective therapy or standard of care exists;
4. Dose expansion phase: Histologically or cytologically documented, locally advanced or metastatic BTC that has progressed on standard first line chemotherapy (Arm A), low-to-intermediate grade (G1 or G2), well-differentiated, unresectable or metastatic pNET that has progressed on everolimus, sunitinib, or both (Arm B), low-to-intermediate grade (G1 or G2), well-differentiated, unresectable or metastatic epNET that has progressed on everolimus (Arm C), and advanced STS (of the subtypes listed below) that has progressed on at least one line of standard therapy (if available) or refused standard frontline cytotoxic chemotherapy will be evaluated for enrollment;

NET expansion patients must also meet the following criteria:

- a. Gastroenteropancreatic NETs (GEP-NETs) or NETs of origins other than the lung or thymus (including unknown origins), with a mitotic rate of \leq 20/10 high powered field (HPF) and/or a Ki-67 proliferative index of \leq 20%; if the mitotic rate and Ki-67 index indicated different grades, the higher grade is used to assign classification; or
- b. NETs of the lung or thymus with a mitotic rate of \leq 10/10 HPF;

STS subtype eligible to be enrolled:

- i. Leiomyosarcoma (LMS)
- ii. Undifferentiated pleomorphic sarcoma (UPS)
- iii. Epithelioid sarcoma
- iv. Angiosarcoma
- v. Pigmented villonodular synovitis (PVNS)
- vi. Synovial sarcoma (SS)

5. Patients taking a somatostatin analogue (SSA) to control symptoms of functioning pNET or epNET will be permitted to enroll in the study provided that they have been on a stable SSA regimen for at least 2 months before enrollment and will continue on this regimen during the study;
6. Patients taking SSAs in the absence of secretory symptoms must also have been treated with everolimus (pNET or epNET) or sunitinib (pNET) in order to be eligible for this study. Since disease progression is a requirement for enrollment

in the dose expansion phase, in such cases both the targeted therapy (everolimus and sunitinib) and the SSA must be discontinued at least 4 weeks before the first dose of study drug.

7. Patients must have measurable disease (according to RECIST Version 1.1);
8. Patients must have radiological documentation of progression of disease in the last 12 months prior to the initiation of study drug;
9. ECOG performance status of 0 or 1;
10. Expected survival of more than 12 weeks;
11. For female patients of childbearing potential and male patients with partners of childbearing potential, agreement (by patient and partner) to use a highly effective form(s) of contraception, that results in a low failure rate (<1% per year) when used consistently and correctly, starting during the screening period, continuing throughout the entire study period, and for 90 days after taking the last dose of study drug. Such methods include: oral hormonal contraception (combined estrogen/progestogen, or progestogen-only), associated with inhibition of ovulation together with another additional barrier method (e.g., diaphragm, always containing a spermicide), intrauterine device (IUD), intrauterine hormone-releasing system (IUS), bilateral tubal ligation, vasectomized partner (on the understanding that this is the only one partner during the whole study duration), or sexual abstinence. Oral contraception should always be combined with an additional contraceptive method (i.e., barrier method) because of a potential interaction with the study drug. The same rules are valid for male patients involved in this clinical trial if they have a partner of childbearing potential. Male patients must always use a condom. A woman is considered to be of childbearing potential if she is postmenarcheal, has not reached a postmenopausal state (ie, ≥ 12 continuous months of amenorrhea with no identified cause other than menopause), and has not undergone surgical sterilization (removal of the ovaries and/or uterus).

6.2 Exclusion Criteria

Patients will be excluded from the study, if any of the following criteria is met:

1. Patients with high-grade (G3) neuroendocrine tumor, even if it is well differentiated;
2. Absolute neutrophil count (ANC) of $< 1.5 \times 10^9/L$, or platelet count of $< 100 \times 10^9/L$, or hemoglobin $< 9 \text{ g/dL}$;
3. Serum total bilirubin > 1.5 times the upper limit of normal ($\times \text{ULN}$);
4. ALT or AST $> 1.5 \times \text{ULN}$ without hepatic metastases or ALT or AST $> 3 \times \text{ULN}$ with hepatic metastases;
5. Serum potassium, calcium, or magnesium levels out of normal laboratory range, and clinically significant in the investigator's judgment;
6. Creatinine clearance $< 60 \text{ mL/min}$ on the basis of either 24-hour urine collection or the glomerular filtration rate estimated by Cockcroft-Gault equation:

$$\begin{aligned} & [(140 - \text{age}) \times (\text{weight in kg}) \times 0.85 \text{ if female}] \div \\ & [72 \times (\text{serum creatinine in mg/dL})] \end{aligned}$$

7. Urine protein $\geq 2+$; patients discovered to have $\geq 1+$ proteinuria on dipstick urinalysis at baseline should undergo a 24-hour urine collection and must demonstrate ≤ 1 g of protein in 24-hour urine;
8. Uncontrolled hypertension, defined as: systolic blood pressure ≥ 140 mmHg and/or diastolic blood pressure ≥ 90 mmHg;
9. International Normalized Ratio (INR) >1.5 or activated partial thromboplastin time (aPTT) $>1.5 \times$ ULN, unless the patient is currently receiving or intending to receive anti-coagulants for therapeutic purposes;
10. Risk of or active hemorrhage; history of: active gastric/duodenal ulcer or ulcerative colitis; active hemorrhage of an unresected gastrointestinal tumor; history of gastrointestinal perforation or fistulas; or any other condition that could possibly result in gastrointestinal tract hemorrhage or perforation within 6 months prior to first dose of study drug;
11. History of severe hemorrhage from any other site (eg, hemoptysis or hematemesis) within 2 months prior to first dose of study drug;
12. History of thromboembolic event (including deep vein thrombosis [DVT], pulmonary embolism [PE], stroke and/or transient ischemic attack [TIA]) within 6 months prior to the first dose of study drug;
13. Patients with squamous non-small cell lung cancer (NSCLC);
14. Clinically significant cardiovascular disease, including but not limited to, acute myocardial infarction within 6 months prior to enrollment, severe/unstable angina pectoris or coronary artery bypass grafting, New York Heart Association Class III/IV congestive heart failure, ventricular arrhythmias requiring treatment or left ventricular ejection fraction (LVEF) $<50\%$;
15. Mean corrected QT interval by Fridericia's formula (QTcF) >480 msec or any factors that increase the risk of QTc prolongation or risk of arrhythmic events such as hypokalemia, congenital long QT syndrome, family history of long QT syndrome or unexplained sudden death under 40 years of age in a first-degree relative;
16. Concomitant use of any medication known to cause QT prolongation or torsades de pointes (See the table in [Appendix 6](#); see full list at <http://www.qtdrugs.org/>);
17. Systemic anti-neoplastic therapies within 5 half-lives or 4 weeks (whichever is shorter) prior to the first dose of study drug, including chemotherapy, radical radiotherapy, hormonotherapy, biotherapy and immunotherapy;
18. Administration of SSAs in the absence of secretory symptoms must be discontinued at least 4 weeks before the first dose of study drug;
19. Systemic small molecule targeted therapies (eg, tyrosine kinase inhibitors) within 5 half-lives or 4 weeks (whichever is shorter) prior to the first dose of study drug;
20. Palliative radiotherapy for bone metastasis/lesion within 2 weeks prior to the first dose of study drug;
21. Use of strong inducers or inhibitors of CYP3A4 within 2 weeks before the first dose of study drug (3 weeks for St John's Wort).
22. Brachytherapy (ie, implantation of radioactive seeds) within 60 days prior to the first dose of study drug;
23. Surgery or invasive procedure (ie, procedure that include a biopsy), or unhealed surgical incision, within 60 days prior to the first dose of study drug;
24. Toxicity from a previous anti-tumor treatment that does not return to Grade 0 or 1 (except for alopecia);
25. Known human immunodeficiency virus (HIV) infection;

26. Known clinically significant history of liver disease, including active viral or other hepatitis, current alcohol abuse, or cirrhosis. For patients with evidence of chronic hepatitis B virus (HBV) infection, the HBV viral load must be undetectable on suppressive therapy, if indicated. Patients with a history of hepatitis C virus (HCV) infection must have been treated and cured. Patients with HCV infection who are currently on treatment are eligible if they have an undetectable HCV viral load;
27. Evidence of ongoing or active infection requiring intravenous antibiotics;
28. Women who are pregnant or lactating;
29. Brain metastases and/or spinal cord compression untreated with surgery and/or radiotherapy, and without clinical imaging evidence of stable disease for 14 days or longer; patients requiring steroids within 4 weeks prior to start of study treatment will be excluded;
30. Inability to take medication orally, dysphagia or an active gastric ulcer resulting from previous surgery or a severe gastrointestinal disease, or any other condition that investigators believe may affect absorption of the investigational product;
31. Received investigational treatment in another clinical study within 4 weeks prior to the initiation of investigational treatment;
32. Other disease, metabolic disorder, physical examination anomaly, abnormal laboratory result, or any other condition that investigators suspect may prohibit use of the investigational product (ie, hypersensitivity to excipients of the study drug), affect interpretation of study results, or put the patient at high risk.

7 STUDY TREATMENT

7.1 Investigational Product

7.1.1 Investigational Product Supply

Surufatinib will be supplied by Hutchison MediPharma Limited.

7.1.2 Drug Formulation and Specification

Hutchison MediPharma Limited authorizes Shanghai STA Pharmaceutical Product Co., Ltd. (ie originally WuXi AppTec (Shanghai) Co., Ltd) to manufacture and package surufatinib capsules. The technical guidance and quality assurance will be conducted by Hutchison MediPharma Limited. The drug information is provided in Table 4.

Table 4 Drug Formulation and Strength

Formulation	Strength	Route of Administration	Manufacturer
Capsule	50 mg	Oral	Shanghai STA Pharmaceutical Product Co., Ltd.
Capsule	200 mg	Oral	Shanghai STA Pharmaceutical Co., Ltd.

7.1.3 Packaging and Drug Labeling

The investigational drug is packaged in white HDPE bottle with 50 capsules per bottle (old formulation, PD-012-023) or 30 capsules per bottle (new formulation, PD-012-042).

The following information will appear on the label affixed to either the bottle or carton; additional information may be added as required:

- Sponsor identification
- Protocol number
- Drug identification
- Quantity of contents
- Storage conditions
- Dosing instructions
- Route of administration
- Blank spaces to write the patient's identification number
- Finishing lot #

7.1.4 Drug Storage

Study drugs should be sealed and stored in a secure, limited access area between 10°C to 30°C, protected from light and moisture. Surufatinib capsule should not be used beyond expiration date provided by the manufacturer.

The temperature log should be recorded and filed in the study binder.

7.1.5 Drug Accountability

All study drug required for this study will be provided by Hutchison MediPharma. The recipient will acknowledge receipt of the drug by returning the appropriate documentation form indicating shipment content and condition. Damaged supplies will be replaced.

Accurate records of all study drug received at, dispensed from, returned to and disposed by the study site should be recorded by using the Drug Inventory Log.

Study drug will be either disposed of at the study site according to the study site's institutional standard operating procedure or returned to Hutchison MediPharma with the appropriate documentation, as determined by the study site. If the study site chooses to destroy study drug, the method of destruction must be documented.

7.1.6 Dose and Administration

If baseline (pre-dose) PK blood samples need to be collected on the days of PK sample collection, patients must take the investigational product after sampling.

It is recommended that surufatinib be taken with 200 mL water within 1 hour after breakfast. The administration time should be accurately recorded on the day of PK sampling.

For patients treated with surufatinib under new formulation, the minimum number of capsules will be administrated in combination of two strengths (50 mg and 200 mg), eg for 300 mg QD dose, one 200 mg capsule and two 50 mg capsules will be administrated; for 400 mg QD dose, two 200 mg capsules will be administrated, etc. For patients enrolled in the European Union, only 50 mg capsules will be available.

On the day of PK sampling, patients should avoid high-fat, high-calorie meals for the entire day. No caffeine containing foods or drinks, no grapefruit or grapefruit juice, tobacco and tobacco containing products, or alcohol or recreational drugs will be allowed during the PK assessment period (Cycle 1).

If patients miss a dose in the morning, a replacement dose can be taken before 10 pm on the same day. Otherwise, the patient should not make up the missed dose, but should resume scheduled doses the next day per the protocol. The missed dose should be reported to investigators and recorded in the CRF.

7.1.7 Important Safety Risks

The important Identified Risks reported for patients who have received surufatinib may be found in the current version of the surufatinib IB.

7.1.8 Important Potential Risks

The important potential risks of surufatinib include the following: infection, intestinal obstruction, gastrointestinal perforation, myocardial ischaemia, cardiac failure, venous thromboembolism, arterial thromboembolism, and pancreatitis. One patient in the 2015-012-00US1 trial experienced grade 3 PRES, which was deemed related to study drug and was considered resolved. For more information, please see surufatinib IB.

7.2 Dose Modification

7.2.1 General Dose Adjustment Note

The severity of AEs will be graded according to the NCI CTCAE v. 4.03. Reasons for dose modifications or delays, the supportive measures taken, and the outcome will be documented in the patient's chart and recorded in the CRF.

- For any concomitant conditions already apparent at baseline, the dose modifications will apply according to the corresponding shift in toxicity grade, if

the investigator feels it is appropriate. For example, if a patient has Grade 1 asthenia at baseline that increases to Grade 2 during treatment, this will be considered a shift of one grade and treated as Grade 1 toxicity for dose-modification purposes.

- For toxicities that are considered by the investigator to be unlikely to develop into serious or life-threatening events, treatment will be continued at the same dose without reduction or interruption. In addition, no dose reductions or interruptions will be required for anaemia (non-haemolytic) because it can be satisfactorily managed.
- To recover from acute toxicity, unless otherwise indicated, the treatment can be delayed for up to 21 days. If a treatment delay longer than 21 days is required, the patient should be discontinued from the study drug. Continuation/resumption of surufatinib treatment after an interruption of more than 21 days must be discussed with the medical monitor or his or her designee.
- Where several toxicities with different grades or severity occur at the same time, the dose modifications should be according to the highest grade observed.

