7.2.2 Dose Modification Guidance

The dose modification sequence by starting dose is shown in Table 5. A patient is normally allowed to have dose reductions no more than twice, e.g. dose reductions from 300 mg QD to 250 mg QD and then 200 mg QD or from 400 mg QD to 300 mg QD and then 200 mg QD is allowed. However, if the investigator judges that a dose lower than 200 mg QD is required for safety reasons, and that the patient could still benefit from study drug treatment at such a lower dose, then the dose may be further lowered to 200 mg QD, 3 weeks on and 1 week off, during each subsequent 4-week cycle.

Table 5 Dose Modification Sequence by Starting Dose

Daily Starting Dose	300 mg	400 mg**
-1 Dose	250 mg	300 mg
-2 Dose	200 mg	200 mg
-3 Dose*	200 mg on reduced schedule*	200 mg on reduced schedule*
	Off study drug	Off study drug

*Dosing schedule 200 mg QD, 3 weeks on/1 week off, every 28-day cycle.

**No new patients will be enrolled at the 400 mg QD dose.

Dose reduction guidelines for hematologic and non-hematologic toxicities other than hypertension, proteinuria, liver function impairment and hemorrhage are shown in [Table 6](#). In principle, treatment should be held until AE/toxicity resolves or improves to \geq Grade 1. If a patient has a Grade 3 toxicity that is expected to be manageable and reversible with a dose reduction, treatment should be held until toxicity resolves to \leq Grade 1. Patients with Grade 3 non-haematologic toxicity that does not resolve to \leq Grade 1 within 3 weeks should permanently discontinue the study drug.

Table 6 Dose Modification for Hematologic and Non-Hematologic Toxicities

NCI CTCAE v4.03 Toxicity Grading	Action
Grade 1 or 2	None
Grade 3 or 4	
Expected manageable/reversible with dose reduction	Hold ^a
Toxicity remains Grade 3 >7 days	Discontinue treatment
Toxicity lasts ≤7 days and resolves to ≤Grade 1	Reduce 1 dose level
Reoccurrence of Grade 3 toxicity	Reduce 1 dose level or discontinue treatment ^a
Reoccurrence of Grade 4 toxicity	Discontinue treatment
Not expected manageable/irreversible with dose reduction	Discontinue treatment

^a Treatment should be withheld until toxicity recovers to ≤Grade 1. For patients who cannot recover within 21 days, the study drug should be discontinued permanently.

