7.2.3 Dose Modification for Important Identified Risks

Dose modifications for important identified risks are provided in Table 7 (hypertension), [Table 8](#) (proteinuria), [Table 9](#) (liver function impairment), and [Table 10](#) (hemorrhage).

Table 7 Dose Modification for Hypertension

Grade and Definition	Dose Modification	Suggested Actions
Grade 1: prehypertension (systolic BP120-139 mmHg or diastolic BP 80-89 mmHg)	None.	None.
Grade 2: Stage 1 hypertension (systolic BP140-159 mmHg or diastolic BP 90-99 mmHg); medical intervention indicated; recurrent or persistent(≥24 hours); symptomatic increase by >20 mmHg (diastolic) or to >140/90 mmHg if previously within normal range; monotherapy indicated	None.	Treatment target: control blood pressure to below 140/90 mmHg. If patient has already received antihypertensive treatment at baseline, the dose should be increased or treatment changed. If patient did not receive treatment at baseline, monotherapy should be administered. Refer to relevant anti-hypertensive treatment guidelines for dose administration and modification and consult cardiologist if necessary.
Grade 3: Stage 2 hypertension (Systolic pressure ≥ 160mmHg or diastolic pressure ≥ 100mmHg); medical intervention indicated; more than one drug or more intensive therapy than previously used indicated	If BP >160/100mmHg lasts for >3 days after initiation of anti-hypertensive treatment or modification of current anti-hypertensive treatment, surufatinib treatment should be held. If hypertension resolves to Grade 1 or baseline level within 21 days, sulfatinib treatment could be re-started at a lower dose level.	Treatment target: control blood pressure below 140/90 mmHg. Initiate antihypertensive treatment, increase dose of current treatment, or add other treatments. For use and adjustment of antihypertensive treatment, refer to relevant treatment guidelines or consult cardiologist if necessary.

Table 7 Dose Modification for Hypertension

Grade and Definition	Dose Modification	Suggested Actions
Grade 4: Life-threatening consequences (e.g., malignant hypertension, transient or permanent neurologic deficit, hypertensive crisis); urgent intervention indicated	Discontinue surufatinib treatment.	Emergent medical intervention.

Table 8 Dose Modification for Proteinuria

Grade and Definition	Dose Modification	Suggested Actions
Grade 1: 1+ proteinuria; urinary protein <1.0 g/24 hours	None.	Follow up as planned schedule.

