Grade 2: 2+ or 3+ proteinuria; urinary protein 1.0 - 2.0 g (excluding 2.0 g)/24 hours	None.	Provide supportive treatment and increase the frequency of urine monitor to once a week; consult nephrologist if necessary.
Grade 2: Proteinuria \geq 2+; urinary protein 2.0 - 3.5 g (excluding 3.5 g)/24 hours	Hold surufatinib treatment and resume treatment at the same dose level if proteinuria resolves to \leq Grade 1 within 21 days	Provide supportive treatment and increase the frequency of urine monitor to once a week; consult nephrologist if necessary.
Grade 3: Urinary protein \geq 3.5 g/24 hours	Hold surufatinib. If test results resolves to \leq Grade 1 within 21 days, resume at a lower dose.	Provide supportive treatment and increase the frequency of urine monitor to once or twice a week; consult nephrologist if necessary.

^a If urine dipstick reveals proteinuria 2+, 24-hour urine collection should be performed for determination of total protein within one week. The CTCAE grade recorded for proteinuria should be determined by the 24-hour urine collection, however the start date of the AE will be recorded as the first instant of proteinuria (i.e. urine dipstick). If surufatinib dose has been reduced to 200mg QD and a further dose reduction is required for recurrent proteinuria, keep the same daily dose of 200 mg QD of surufatinib for 3 consecutive weeks followed by 1-week drug holiday and repeat for each treatment cycle, (i.e. 3 weeks on and 1 week off; every 4 weeks constitutes a treatment cycle). If proteinuria cannot resolve to \leq Grade 1 after a dose interruption of 21 days, continuation/resumption of surufatinib treatment should be discussed with the medical monitor. Surufatinib treatment should be discontinued if a patient develops nephrotic syndrome.

Table 9 Dose Modification for Liver Function Impairment

Grade and Definitions	Dose Adjustment	Suggested Actions
Grade 1: ALT >1-3 \times ULN or AST >1-3 \times ULN	None.	Follow up per planned schedule. Check total bilirubin. ^a
Grade 2: ALT >3-5 \times ULN or AST >3-5 \times ULN	Maintain the original dose, provide supportive care of complications of liver impairment, observation for 1 week, If the ALT and AST is	Check total bilirubin. ^a Provide supportive care and increase the frequency of liver function monitor to 1-2 times a week.

Table 9 Dose Modification for Liver Function Impairment

Grade and Definitions	Dose Adjustment	Suggested Actions

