	stable or declining, continue with the original dose treatment; If the ALT and/or AST continue to rise significantly, then interrupt surufatinib; resume treatment at a lower dose if transaminase elevation resolves to \leq Grade 1 within 21 days; otherwise discontinue treatment.	
Grade 3: ALT $>5 \times$ ULN or AST $>5 \times$ ULN	Hold surufatinib; resume treatment at the lower dose if resolves to \leq Grade 1 within 21 days; otherwise discontinue treatment.	Check total bilirubin. ^a Provide supportive care and increase the frequency of liver function monitor to twice a week; consult expert if necessary.
Grade 4: ALT $>20 \times$ ULN or AST $>20 \times$ ULN	Discontinue treatment.	Check total bilirubin. ^a Urgent medical intervention indicated.

^a If ALT or AST escalates to 3 times baseline level with bilirubin $>2 \times$ ULN, the biochemical criteria for Hy's Law have been met, surufatinib should be discontinued immediately, and the event should be reported to the sponsor within 24 hours. See [Appendix 7](#) for important additional information.

Table 10 Dose Modification for Hemorrhage

Grade and Definitions	Dose modification	Suggested Actions
Grade 1	None.	Follow up per planned schedule.
Grade 2	Hold surufatinib treatment; Resume at a lower dose if resolves to \leq Grade 1 within 21 days.	Active management.
Grade 3 or higher	Discontinue treatment.	Immediate medical intervention to identify and treat the source of bleeding.

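### Protocol 7.2.1's general dosing notes and Tables 6 to 9 can give different actions for the same event, with no stated order of precedence

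*Protocol*

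**What the plan says.** Protocol 7.2.1 is a list of general notes. Three matter here.

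- **Baseline shift.** For a condition already present at baseline, "the dose modifications will apply according to the corresponding shift in toxicity grade", if the investigator thinks this appropriate. In its example, Grade 1 asthenia rises to Grade 2, and "this will be considered a shift of one grade and treated as Grade 1 toxicity for dose-modification purposes".
- **Low-risk toxicities.** Where the investigator considers a toxicity unlikely to become serious or life-threatening, "treatment will be continued at the same dose without reduction or interruption". No grade limit is given and no table is mentioned.
- **Anaemia.** The same bullet adds that "no dose reductions or interruptions will be required for anaemia (non-haemolytic"), because it can be managed.

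Protocol 7.2.2 introduces Table 6 as "Dose reduction guidelines for hematologic and non-hematologic toxicities" and excepts four: hypertension, proteinuria, liver function impairment and hemorrhage. A Grade 3 or 4 toxicity is held if it is expected to be manageable or reversible with a dose reduction, and otherwise discontinued. After a hold, Table 6 lowers the dose one level if the event resolves within 7 days, and discontinues if Grade 3 lasts longer.

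Protocol 7.2.3 covers the excepted toxicities in Tables 7 to 10. The action rows of Tables 7 to 9 are set mainly by absolute values (mmHg, g/24 h, multiples of ULN). For Grade 4 hypertension, Table 7 says "Discontinue surufatinib treatment". For Grade 2 ALT or AST, Table 9 says "Maintain the original dose, provide supportive care of complications of liver impairment", with further steps if values keep rising. For Grade 3 it says "Hold surufatinib; resume treatment at the lower dose if resolves to" Grade 1 or lower within 21 days.

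**The concern.** Two sites can act differently on the same event, and each can point to a sentence in the protocol. That is a safety matter. Section 2.3 reports Grade 3 or higher hypertension and proteinuria each in more than 10% of monotherapy patients. Section 3.3 rests its statement that risks are mitigated on 7.2.2 and 7.2.3 and does not mention the notes in 7.2.1.

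It also affects what is reported. Protocol 10.3 and SAP Section 15 summarise reductions, interruptions and relative dose intensity; SAP 17.1.2 and 17.1.3 summarise events leading to discontinuation or dose adjustment. Section 5.1.2 gives confirming tolerability at the RP2D as an aim of the expansion phase. These figures would depend partly on which passage a site followed.

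**Working it through.** The plan gives no figure to reproduce. The check sets the passages side by side.

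**1. Low-risk note against Table 6.** Take a Grade 3 non-hematologic event that the investigator expects to be manageable and thinks unlikely to become serious. Under 7.2.1 the dose continues unchanged. Under 7.2.2 and Table 6 it is held, then lowered one level or stopped. The event meets both descriptions at once, so the instructions are opposite. The hold rows of Tables 7 to 9 raise the same question.

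**2. Anaemia note against Table 6.** Anaemia is hematologic and is not among the four exceptions, so Grade 3 or 4 non-haemolytic anaemia falls in the hold-or-discontinue rows. Under 7.2.1 no change is required.

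**3. Baseline shift against Tables 6 to 9.** Section 6.2 admits patients in the Grade 1 range of Tables 7 to 9:

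- blood pressure below 140/90 mmHg (criterion 8; Table 7 Grade 1 is 120-139 or 80-89)
- 1+ dipstick protein with no more than 1 g/24 h (criterion 7; Table 8 Grade 1 is below 1.0 g)
- ALT or AST up to 1.5 x ULN, or up to 3 x ULN with hepatic metastases (criterion 4; Table 9 Grade 1 is >1-3 x ULN)

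Following the asthenia example, grade used = on-study grade minus baseline grade. From baseline Grade 0 nothing changes. From baseline Grade 1:

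| Table | On study | Action as printed | Grade used | Action as shifted |
|---|---|---|---|---|
| 6 | Grade 3, manageable | Hold, then one level lower; discontinue if >7 days | 3 - 1 = 2 | None |
| 7 | Grade 3, >160/100 mmHg for >3 days despite treatment | Hold; lower dose on restart | 3 - 1 = 2 | None |
| 7 | Grade 4 | Discontinue | 4 - 1 = 3 | Grade 3 row |
| 8 | Grade 2, 2.0 to <3.5 g/24 h | Hold; same dose on resuming | 2 - 1 = 1 | None |
| 8 | Grade 3, >=3.5 g/24 h | Hold; lower dose on resuming | 3 - 1 = 2 | Undefined: two Grade 2 rows (none, or hold) |
| 9 | Grade 3, >5 x ULN | Hold; lower dose on resuming, otherwise discontinue | 3 - 1 = 2 | Maintain, observe 1 week, interrupt if still rising significantly |
| 9 | Grade 4, >20 x ULN | Discontinue | 4 - 1 = 3 | Grade 3 row |

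**4. Search for precedence.** Of the 7.2.1 bullets, only the 21-day delay bullet yields to other instructions. The last bullet makes the highest grade govern, but only among concurrent toxicities. No sentence ranks 7.2.1 against the tables.

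**5. Effect on one reported figure (illustration).** Assume a 300 mg patient has a manageable Grade 3 event on Day 8 of Cycle 1, held for 7 days, with treatment resumed on Day 15 at 250 mg (Table 5). SAP 15.1 divides dose per day over the whole period by the planned daily dose.

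- Table 6 route: (7 x 300 + 7 x 0 + 14 x 250) / (28 x 300) = 5,600 / 8,400 = 66.7%
- 7.2.1 route: (28 x 300) / (28 x 300) = 100%

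The same event falls in the SAP's below-80% category or in its 80-120% category, depending on the passage followed.

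**The case against.** The strongest reply is that 7.2.1 is headed as a general note, so the specific tables should prevail. That is a reasonable drafting convention, but the protocol does not state it, and it does not settle every case. On anaemia, 7.2.1 is the more specific text, so the convention would favour the note over Table 6. On low-risk toxicities, it is unclear which text is the more specific.

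The shift note is optional and can be read as a way of choosing the table row, not as a rival to the tables. That stands, and it makes the third conflict conditional. What remains is that the note's reach is unstated, although baseline is written into particular places: Table 7 allows recovery to baseline level, and the Hy's Law footnote to Table 9 uses a multiple of baseline.

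Dose changes and their reasons are recorded in the CRF, so some variation is traceable. However, 7.2.1 asks for reasons for modifications or delays, and a decision to leave the dose alone is neither.

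A reader might infer more than the documents support:

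- **That 7.2.1 always says to continue unchanged.** At Grade 4 in Tables 7 and 9 the shift leads to the Grade 3 row, not to no action. The shifted ALT case still carries observation and possible interruption.
- **That the low-risk note reaches Grade 4.** Section 9.5 describes Grade 4 as life-threatening, so this conflict is essentially about Grade 3.
- **That Table 6 holds every Grade 3 or 4 event.** It discontinues those not expected to be manageable.
- **That a hold for anaemia is forbidden.** The note says only that changes are not required.
- **That bleeding is left open.** Table 10 governs haemorrhage.

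**Conclusion.** The point holds in three parts of unequal strength. The low-risk note and Table 6 conflict outright at Grade 3. The anaemia exemption is missing from a table whose scope includes anaemia. The optional baseline shift has no stated reach and, when used from baseline Grade 1, changes the action in the seven rows worked above.

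The number of patients affected cannot be derived. It depends on how many enter at Grade 1, how often investigators use the shift, and how many Grade 3 events they judge low risk. The 66.7% against 100% comparison is one assumed patient, not an estimate for the trial. The expansion-phase primary endpoints are PFS rates, and nothing here shows that they are invalid. The consequences are for consistent patient management and for comparable tolerability figures. The passages should be reconciled.

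How long a Grade 3 event may last before treatment stops is a separate question, not addressed here.

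**What to change.** In the next amendment or a dosing clarification letter, reconcile 7.2.1 with Tables 6 to 9 by stating:

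1. an order of precedence between the general notes and the tables;
2. whether the low-risk note and the anaemia note override Table 6 at Grade 3 or Grade 4, with a matching cross-reference in the Table 6 scope sentence;
3. for each table, whether the baseline-shift option applies and at which grades, including which Grade 2 row of Table 8 is meant if it does.

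The choice of rule belongs to the sponsor's clinical team, and none is proposed here. The cost is a few sentences, with no new procedures, data or patients.
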